3.2 Study Endpoints

3.2.1 Primary endpoint

Change in antibody titer response to vaccination, as measured by microneutralization titers at day 0 and day 70 and its relationship with novel baseline biomarkers.

3.2.2 Secondary endpoints

- Change in antibody titer response to vaccination, as measured by microneutralization titers at day 0 and day 70 and its relationship with established baseline biomarkers (CD38⁺ CD20⁺ B cell frequencies and/or transcriptomic signatures) and post-vaccination biomarkers (plasmablast cell frequencies and/or transcriptomic signatures)
- Difference in antibody titer response to vaccination between subjects with a history of symptomatic or asymptomatic SARS-CoV-2 infection and those with no evidence of SARS-CoV-2 infection

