2.2 Secondary Objectives

- Validate the findings of prior study 09-H-0239, specifically the relationship between cell populations and/or gene transcripts at baseline and after vaccination that correlate with vaccine immune response
- Evaluate the effect of prior SARS-CoV-2 infection on the antibody response to the seasonal influenza vaccine in healthy volunteers

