3.1 Description of the Study Design

This is a prospective, open-label, exploratory study to evaluate the baseline immune state and post-vaccination immune responses of healthy volunteers to the seasonal influenza vaccine. The study vaccine is approved and indicated by the US Food and Drug Administration (FDA) for active immunization for the prevention of influenza disease caused by influenza virus subtypes A and B. Blood samples will be collected at various timepoints before and up to 100 days after vaccination to explore short- and long-term immunological effects of immunization. Blood may also be collected at optional monthly study visits up until 1 year after vaccination. Subjects may optionally provide stool samples on days -7, 0, 28, and 100.

Subjects will remain on study and may optionally repeat study visits (including vaccination) annually through the 2023-24 influenza season, with final study follow-up up to 1 year after vaccination. Sampling individual subjects across several influenza seasons will allow us to monitor for multi-season responses.

Blood will be evaluated to characterize immune response parameters, primarily changes in antibody titers following vaccination. These evaluations will be used to assess expected response to the vaccination in order to identify baseline and early response correlates of vaccination responses (e.g., by searching among the many parameters we will measure, as listed in section 7.2). Other important immune response parameters include the frequency of peripheral monocytes and interferon transcriptomic signatures (past studies suggest both can be detected in the blood on day 1 following influenza vaccination), as well as the frequency of plasmablast and certain CD4⁺ T-cell subsets (detectable around day 7 in past studies with influenza vaccination). In this study, these parameters should be captured exactly on days 1 and 7, as the earlier CHI study of influenza vaccination demonstrated that measuring these on the specified days will minimize variability and maximize detection of biologically important signals.³ Additional research evaluations may include flow cytometry and transcriptome and genetic analyses.

In year 2 of this protocol, enrollment will be enriched according to history of SARS-CoV-2 infection. We will enroll up to 120 subjects by consecutive sampling in the following cohorts:

- Up to n=40 subjects with no history of SARS-CoV-2 infection, as determined by a negative antibody test at screening.

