- Up to n=40 subjects with confirmed symptomatic SARS-CoV-2 infection, as determined by a documented positive polymerase chain reaction (PCR) test, and a positive antibody test at screening.
- Up to n=40 subjects with confirmed SARS-CoV-2 antibodies at screening or from an FDA-approved test as documented by the subject but with no history of symptoms.

This design will allow comparison between cohorts to explore the long-term immunological effects of SARS-CoV-2 infection. Recruitment in year 2 will be targeted toward these groups, and enrollment for each cohort will be stopped when its sample size is achieved for the year.

Because the vaccine response to the seasonal influenza vaccine in AA people has only started to be explored,¹⁰ we will recruit up to 10 AA subjects (of the 40) for each group described above in order to evaluate the relationship between AA race and vaccine responses in each of the three cohorts above.

Because obesity is associated with decreased vaccine responsiveness,¹¹ we will exclude individuals with a body mass index (BMI) ≥ 30 .

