15.3 Description of the Analyses

The primary analysis will be to correlate multiple baseline biomarkers with the vaccine-induced outcome adjMFC using GEE to reflect clustering at the subject level due to multiple measurements over multiple years. Analyses will be stratified by year by including a separate term for each cohort year in the GEE models. Two-sided testing will be performed with an adjustment for multiplicity such as the Bonferroni to control the overall type I error rate at 0.05.

For the first secondary analysis, a similar analysis strategy will be used as in the primary analysis, but the relationship between the vaccine-induced outcome adjMFC and baseline biomarkers (specifically ID_96 [CD38⁺ CD20⁺ B cell frequencies and/or transcriptomic signatures]) and post-vaccination biomarkers (specifically ID_87 [plasmablast cell frequencies and/or transcriptomic signatures]) will be examined separately. Specifically, we will evaluate 1) whether the slope between adjMFC and ID96_0 (measured at day 0) is zero using GEE, as described for the primary analysis with no adjustment for multiplicity, and 2) whether the slope between adjMFC and ID_87, measured at day 7/day 0) is zero using GEE, as described for the primary analysis with no adjustment for multiplicity. Both analyses are designed to replicate findings from 09-H-0239.³

Analysis of the secondary endpoint on SARS-CoV-2 will involve comparing the results of the above analyses by cohort: 1) those subjects with prior symptomatic SARS-CoV-2 infection, 2) those subjects with prior asymptomatic SARS-CoV-2 infection, and 3) those subjects without a history of SARS-CoV-2 infection.

The exploratory analyses will involve both unsupervised and supervised analyses using the framework developed in 09-H-0239. In addition to that framework, under this protocol we will be able to characterize immune responses and biomarker relationships over multiple seasons in the same individual. The first general aim is to perform unsupervised analysis of the immune states of the baseline along the measured phenotypic dimensions, including PBMC/cell subset

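### The SARS-CoV-2 secondary endpoint asks for titer response in infected versus uninfected subjects, but Section 15.3 only compares biomarker analyses across three cohorts and never names that contrast

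*Combined protocol and SAP*

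**What the plan says.** - **Objective (Section 2.2).** The second secondary objective is: "Evaluate the effect of prior SARS-CoV-2 infection on the antibody response to the seasonal influenza vaccine in healthy volunteers". Infection is a single exposure here, not split by symptoms.
- **Endpoint (Section 3.2.2, repeated in the Protocol Summary).** The comparison is drawn "between subjects with a history of symptomatic or asymptomatic SARS-CoV-2 infection and those with no evidence of SARS-CoV-2 infection". The outcome is titer response, and the natural reading is two groups.
- **Design (Section 3.1).** Year-2 enrollment fills three cohorts: "Up to n=40 subjects with no history of SARS-CoV-2 infection", "Up to n=40 subjects with confirmed symptomatic SARS-CoV-2 infection", and up to 40 antibody-positive subjects without symptoms. The section says that this allows cohorts to be compared in order to explore long-term effects of infection.
- **Analysis (Section 15.3).** "Analysis of the secondary endpoint on SARS-CoV-2 will involve comparing the results of the above analyses by cohort". The listed groups are the symptomatic cohort, then "2) those subjects with prior asymptomatic SARS-CoV-2 infection, and 3) those subjects without a history of SARS-CoV-2 infection". The analyses referred to are the GEE regressions of adjMFC on baseline and post-vaccination biomarkers.
- **Elsewhere.** Section 15.1 leaves the SARS-CoV-2 objective out of its list. Section 15.2 gives power only for a biomarker slope. No section states a test, alpha or multiplicity rule for the SARS-CoV-2 endpoint.

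**The concern.** The analysis differs from the endpoint in two respects. The endpoint has two groups and the analysis has three, with no rule for combining the infected cohorts. The endpoint's outcome is titer response, whereas the analyses to be compared by cohort are biomarker relationships.

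The stated question, whether prior infection changes the response to influenza vaccine, could therefore go without a single pre-specified answer. If the symptomatic cohort differed from the uninfected and the asymptomatic cohort did not, the plan has no rule for what to conclude about prior infection. The analyst would be free to choose the contrast after seeing the data.

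**Working it through.** **1. Does any section supply the contrast?**

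| Section | Outcome | Groups |
|---|---|---|
| 2.2 | antibody response | prior infection as one exposure |
| 3.2.2 and Protocol Summary | titer response | any infection versus no evidence |
| 15.1 | SARS-CoV-2 not mentioned | none |
| 15.2 | adjMFC on a biomarker | none |
| 15.3 | biomarker analyses of adjMFC | three cohorts, compared by an unnamed method |

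No row after 3.2.2 gives titer response for infected versus uninfected subjects.

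**2. The plan's own power figure.** Table 2 at N=170, effective n=153, alpha 0.05/50=0.001:
- SE = sqrt(2.09/(152×3.03)) = 0.0674
- 0.29/0.0674 = 4.305
- Power = Φ(4.305−3.291) = .845, against the stated .85

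The figure reproduces, but it concerns a biomarker slope and says nothing about a cohort difference.

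**3. Precision of the candidate contrasts.** Inputs: 40 per cohort (Section 3.1, a ceiling) less 10% missing (Table 2) gives 36. Outcome in SD units, one observation per subject, two-sided 5%.
- Pooled, 72 versus 36: SE = sqrt(1/72+1/36) = 0.204
- One infected cohort versus uninfected, 36 versus 36: SE = sqrt(2/36) = 0.236
- Ratio 0.204/0.236 = 0.866

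A three-group model gives the same pooled precision. The average of the two infected means minus the uninfected mean has SE sqrt(1/36 + ¼(1/36+1/36)) = sqrt(1/36+1/72) = 0.204. Splitting the cohorts costs nothing if this contrast is named.

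Detectable difference at 80% power, (1.960+0.842)×SE: 0.57 SD pooled, 0.66 SD pairwise.

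**4. Power when both infected cohorts share the same effect.** The documents give no effect size, so a range is assumed. The 2-df column uses a noncentral chi-square with noncentrality 36×Σ(mean−grand mean)², for example 8.64 at 0.6 SD.

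| Common effect (SD) | Pooled | One pairwise, unadjusted | 2-df three-group |
|---|---|---|---|
| 0.3 | .31 | .25 | .24 |
| 0.4 | .50 | .40 | .40 |
| 0.5 | .69 | .56 | .58 |
| 0.6 | .84 | .72 | .75 |
| 0.8 | .98 | .92 | .95 |

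**5. Power when the effects differ.** The pooled contrast then estimates the average of the two effects. Pairwise power is for the cohort with the larger effect.

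| Effects (SD) | Pooled | Pairwise | 2-df |
|---|---|---|---|
| 0.6 and 0.3 | .60 | .72 | .62 |
| 0.8 and 0.4 | .84 | .92 | .87 |
| 0.6 and 0 | .31 | .72 | .75 |

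Pooled beats the unadjusted pairwise test on the larger effect only if (d1+d2)/2 ÷ 0.204 exceeds d1 ÷ 0.236. That requires d2/d1 > 2×0.866−1 = 0.73.

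**The case against.** **The plan gives up power.** A reader might infer that splitting the infected subjects commits the trial to pairwise tests that share 5% and leave out half of the infected subjects each time. The documents do not support this. Section 15.3 names no test and no alpha for this endpoint, and a three-cohort model can return the pooled contrast at full precision. Even with two Bonferroni-adjusted pairwise tests at a common 0.6 SD, the chance that at least one is significant is .78, against .84 pooled. When the effects differ enough, pooling is the weaker choice. This part of the objection stands, and power is not the main ground for the point.

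**Three cohorts are the design.** Section 3.1 enrolls three cohorts for comparison, and the endpoint's wording could be read as naming two infected groups, each compared with none. Section 1.2 says that the goal is not to compare groups, and Section 15.2 calls the study hypothesis-generating. These are reasons to keep the three-cohort results and to treat the test modestly. They do not remove a group difference in titer response that Sections 2.2 and 3.2.2 list as a secondary objective and endpoint. Under the alternative reading, Section 15.3 still contains no titer contrast.

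**The sample may not be 36 per cohort.** The 40s are ceilings. On the other side, other enrollment years and repeat seasons could add data through the GEE, since antibody screening in Section 6.1 is not limited to year 2. The figures are therefore illustrative.

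**Conclusion.** The point holds as a mismatch between endpoint and analysis. Followed as written, Section 15.3 does not produce the infected-versus-uninfected difference in titer response that Section 3.2.2 defines, and no other section supplies it. That conclusion rests on the text alone and needs no assumption about effect size.

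The power consequence is secondary and conditional. At an assumed common effect of 0.5 to 0.6 SD, naming the pooled contrast gives 12 to 13 points more power than one unadjusted pairwise test (.69−.56=.13; .84−.72=.12). Against a 2-df test the gain is 9 to 11 points (.84−.75=.09; .69−.58=.11). These figures assume 36 per cohort, one observation per subject, equal variances and similar effects in the two infected cohorts. The gain over a pairwise test on the larger effect is lost once the smaller effect falls below about 73% of the larger. It would be wrong to report that the three-cohort plan loses power in general.

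**What to change.** In Section 15.3:
- Name the difference in adjMFC between infected (symptomatic plus asymptomatic) and no-evidence subjects, from the same GEE framework with the cohort-year term, as the test of this secondary endpoint. Report it with a confidence interval.
- State how the two infected cohorts are weighted if they fill unequally.
- Report the symptomatic, asymptomatic and no-history comparison of adjMFC from the same model alongside it. The by-cohort biomarker analyses can remain as further description.
- Add the SARS-CoV-2 objective to Section 15.1 so that the statistical section matches Section 2.2.

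The cost is a few sentences and one extra contrast, with no added subjects, visits or assays. The downside is that a pooled contrast can hide a weaker, null or opposite effect in one infected cohort and has less power in that case. The three-cohort results must therefore be kept, not replaced.

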3.2.3 Exploratory endpoints

Exploratory assessments may include, but are not limited to, pre- and post-vaccination evaluation of:

- Frequency of leukocytes (to include lymphocyte subsets) in peripheral blood as analyzed by complete blood count (CBC) with differential and clinical and research flow cytometry.
- Cellular transcriptional activity in immune cell subsets as analyzed by RNA-seq or microarrays.
- Whole blood transcriptome as analyzed by RNA-seq.
- Single-cell transcriptome as analyzed by RNA-seq or CITE-seq.
- Characterization of extracellular and intracellular proteins by CyTOF.
- Peripheral blood mononuclear cell (PBMC) transcriptome as analyzed by RNA-seq.
- Cellular chromatin accessibility in immune cell subsets as analyzed by the assay for transposase-accessible chromatin using sequencing (ATAC-seq).
- Relative abundance of serum proteins, such as that provided by the SomaLogic SOMAscan assay.
- Serum antibody titers.
- Additional “omics” assays for assessing immune receptor repertoires, profiling molecular states in cells or for quantifying the relative abundance of circulating molecules to assess the state of the immune system, or characterizing the microbiome in healthy volunteers.

4 Study Population

4.1 Recruitment Plan

Healthy adult volunteers will be recruited through the NIH Clinical Research Volunteer Program, the Office of Patient Recruitment, or ResearchMatch. Volunteers will also be recruited from existing NIH protocols, including protocol 18-I-0101 (“Sample Collection From Healthy Volunteers For Assay Optimization”) and protocols that evaluate SARS-CoV-2 infection or

antibodies (e.g., protocol 20I0117, “Surveillance of individuals following SARS-CoV-2 exposure”) to stratify enrollment for SARS-CoV-2 status as described in section 3.1.

Recruitment in year 2 will also target AA volunteers for each cohort (section 3.1). Potential subjects will be identified by discussion between the study teams and review of medical and research records, including results of SARS-CoV-2 testing, if available. Race will be self-identified. A recruitment email will be approved by the IRB before distribution. Interested potential subjects may also contact the study team directly using the NIH email address: [contact].

Local and regional recruitment will be done using internet ad campaigns, social media outlets, print ads, and from local clinics via the NIAID Office of Communications and the NIAID patient recruitment with Matthews Media Group, Inc.

Potential subjects may be contacted by email or telephone to set up a pre-screening phone call to discuss interest, eligibility (including any past SARS-CoV-2 testing), and scheduling prior to the screening visit.

For the convenience of the study (which involves questionnaires) and because this study does not offer benefit to subjects, only English speakers will be recruited.

4.2 Inclusion Criteria

Individuals must meet all of the following criteria to be eligible for study participation:

1. Aged 18 years and older (no upper age limit).
2. Able to provide informed consent.
3. Willing to have samples and data stored for future research.
4. Able to proficiently speak, read, and write English.

4.3 Exclusion Criteria

Individuals meeting any of the following criteria will be excluded from study participation:

1. CBC with differential, lymphocyte phenotyping with T, B, and natural killer cells (TBNK), acute care, mineral, and hepatic panels, anti-CMV immunoglobulin (Ig) G and IgM, and/or anti-Epstein-Barr virus (EBV) antibody panel values outside of the NIH Department of Laboratory Medicine normal reference ranges and deemed clinically significant by the PI at the time of screening.
2. Positive result for anti-HIV 1/2 antibody, antibody to hepatitis B surface antigen, or anti-hepatitis C virus antibody screening at the time of screening.
3. Prior receipt of a current seasonal influenza vaccine (for the season of participation).
4. History of allergy or hypersensitivity to any components of the study vaccine (e.g., egg protein, latex).

5. History of severe reactions to vaccines.
6. Use of an oral glucocorticoid within the past 30 days.
7. Receipt of a live-attenuated vaccine within the past 30 days.
8. Receipt of any experimental vaccine.
9. Receipt of any other type of vaccine (non-live and non-experimental, e.g., tetanus, diphtheria, and pertussis [TDaP]) within the past 14 days.
10. Planned vaccination before day 100 after study vaccination.
11. Current or recent use (within the past 90 days) of immunoglobulin therapy.
12. Surgery within the past 8 weeks, or planned surgery before day 28.
13. Current (within the past 30 days) treatment for active malignancy.
14. Cancer chemotherapy in the past 2 years.
15. Administration of any blood products within 90 days of the screening, or planned administration before day 100.
16. History of parasitic, amebic, fungal, or mycobacterial infections within the past 1 year, with the exception of tinea pedis and onychomycosis.
17. History of autoimmune or autoinflammatory disease.
18. History of a bleeding disorder.
19. Current use (within the past 30 days) of illicit drugs (per subject report), with the exception of marijuana.
20. Current alcohol use disorders (criteria per Diagnostic and Statistical Manual of Mental Disorders, fifth edition), within the past 30 days.
21. Serious, ongoing, uncontrolled infection within the past 30 days as per the judgement of the PI.
22. History of Guillain-Barre syndrome (GBS).
23. BMI \geq 30.
24. Known or suspected immunodeficiency within 1 year, including documented HIV infection.
25. Pregnancy or planning to become pregnant during the study period. (Women of childbearing potential must have a negative urine or serum pregnancy test at screening.)
26. Presence of conditions that, in the judgment of the PI, may put the individual at undue risk or compromise the scientific objectives of the study.

Co-enrollment guidelines: Co-enrollment in other trials is restricted, other than enrollment on observational studies. Consideration for co-enrollment in trials evaluating the use of a licensed medication will require the approval of the PI. Study staff should be notified of co-enrollment on any other protocol as it may require the approval of the PI.

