2.1 Primary Objective

Identify baseline correlates of immune response to the seasonal influenza vaccine in healthy individuals

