6.1 Screening (day -30 to -7)

In the first year of participation, screening will include an in-person health/medication history and physical exam (including height and weight measurement for BMI) as well as the evaluations listed below. For optional participation in subsequent influenza seasons, screening will have the same evaluations but an electronic REDCap health history and medication questionnaire instead of an in-person history/physical, and subjects will be asked their height and weight to estimate BMI. For individuals who report a history of SARS-CoV-2 infection, we will also review COVID-19 symptoms and/or documentation of SARS-CoV-2 testing (from the NIH or outside since December 2019).

The following evaluations will be conducted at the screening visit:

- Urine or serum pregnancy test for women of childbearing potential.
- Blood draw for the following screening tests:
 - CBC with differential.
 - Lymphocyte phenotyping with TBNK.
 - Acute care, mineral, and hepatic panels.
 - Anti-CMV IgG and IgM antibody and anti-EBV antibody panel.
 - Anti-HIV 1/2 antibody, antibody to hepatitis B surface antigen, and anti-hepatitis C virus antibody.
 - SARS-CoV-2 serum antibody test for individuals who do not provide documentation of a positive FDA-approved antibody test result (since December 2019).
 - If an individual with a documented positive SARS-CoV-2 PCR test result is tested for antibodies at screening and the result is negative, antibody testing will be repeated (possibly with a different FDA-approved test). If the second antibody test is negative, the individual will only be eligible to enroll in the cohort with no history of SARS-CoV-2 infection.

If any of these evaluations have been conducted on another protocol at the NIH within the previous 30 days, then they will not be repeated, and those results will be used to determine eligibility on this study. The exception is the pregnancy test, which must be done at the NIH within the previous 2 days. Screening labs conducted under this protocol may be repeated at the discretion of the PI within 30 days.

If the results of any screening tests are consistent with a previously unknown health condition or other incidental findings, then the subject will be informed of the results. The results will also be provided to the subject's primary physician if requested. If the subject does not have a primary

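### Exclusion 2 keys hepatitis B screening to surface antibody: read literally it turns away healthy vaccinated volunteers, and no listed test directly detects current infection

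*Combined protocol and SAP*

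**What the plan says.** Section 4.3 makes every exclusion mandatory: "Individuals meeting any of the following criteria will be excluded from study participation". Item 2 of that list is "Positive result for anti-HIV 1/2 antibody, antibody to hepatitis B surface antigen, or anti-hepatitis C virus antibody screening at the time of screening".

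Section 6.1 gives the matching blood test at screening as "Anti-HIV 1/2 antibody, antibody to hepatitis B surface antigen, and anti-hepatitis C virus antibody", and Appendix A carries the same entry (8 mL at screening). These are the only three places that name a hepatitis B test. None names the surface antigen as the analyte.

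Three other provisions bear on how item 2 works:

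- Item 1 of section 4.3 covers blood counts, lymphocyte phenotyping, chemistry and hepatic panels, and CMV and EBV serology. An out-of-range result there excludes only if "deemed clinically significant by the PI at the time of screening". Item 2 has no such qualifier.
- Item 9 excludes for "Receipt of any other type of vaccine (non-live and non-experimental, e.g., tetanus, diphtheria, and pertussis [TDaP]) within the past 14 days".
- For most screening tests done under another NIH protocol in the previous 30 days, section 6.1 says "those results will be used to determine eligibility on this study".

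The primary objective in section 2.1 is to "Identify baseline correlates of immune response to the seasonal influenza vaccine in healthy individuals".

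**The concern.** Antibody against the surface antigen is what hepatitis B vaccination produces. The documents do not say so, but it is basic immunology and needs no outside figure. A rule that excludes on that antibody therefore removes people for having been successfully vaccinated, and they belong to the healthy population that the primary objective describes.

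The same rule does not do what its position suggests. Hepatitis B sits in one line with HIV and hepatitis C serology, which points to screening for infection. A person who carries the antigen without the antibody would not be identified by any hepatitis B test on the list.

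At stake are who is eligible and how much screening is needed to fill the cohorts. The name of the test matters in use, because results from another NIH protocol can decide eligibility and someone has to match those results to the criterion.

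**Working it through.** **The plan's own figure.** The only related number is the power in Table 2. Section 15.2 gives slope 0.29, var(R) = 2.09, var(X) = 3.03 and two-sided alpha 0.05 with Bonferroni adjustment for 50 comparisons (0.05/50 = 0.001 per test). Table 2 gives an effective n of 153 for N = 170.

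- Standard error: sqrt(2.09 / (152 × 3.03)) = sqrt(2.09 / 460.56) = 0.0674.
- Mean of the Wald statistic: 0.29 / 0.0674 = 4.30; critical value 3.29.
- Power: Phi(4.30 − 3.29) = 0.845, against the stated .85.

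The figure reproduces. It depends on the number enrolled and analysed, not on the number screened, so exclusion 2 does not change it for a given N.

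**The three hepatitis B entries side by side.**

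| Place | Analyte named | Antigen named as analyte? |
|---|---|---|
| Section 4.3, item 2 | antibody to the surface antigen | no |
| Section 6.1, screening list | antibody to the surface antigen | no |
| Appendix A, screening column | antibody to the surface antigen | no |

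Three of three name the antibody and none the antigen. The entries agree with one another.

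**Applying the rules as written to each kind of volunteer.**

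1. *Healthy, hepatitis B vaccine more than 14 days ago, antibody detectable.* Item 9 does not apply, because a licensed non-live vaccine counts only within 14 days. Item 2 applies: the result is positive, there is no judgement clause and no exemption for vaccination. Excluded.
2. *Known current infection, antigen present, antibody absent.* Item 2 is not met. The in-person history and examination in the first year (sections 6.1 and 7.1) could bring the infection to light, and the PI could then act under items 21 or 26. An abnormal hepatic panel could exclude under item 1 if judged clinically significant. All of these routes are indirect.
3. *Undiagnosed current infection, antigen present, antibody absent.* Item 2 is not met and the history would not reveal it. What is left is the examination, the hepatic panel and judgement. No listed test detects the infection directly.

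**If an antigen test is what is actually run**, volunteer 1 is not excluded and volunteers 2 and 3 are tested for directly. The defect is then that the analyte is misnamed in three places.

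**Size.** If a share p of otherwise eligible volunteers had detectable antibody and the rule were applied literally, enrolling 170 would need 170 / (1 − p) such volunteers. The documents give neither p nor the assay used, so no value is put on this.

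**The case against.** The strongest reply is that nothing is shown to have gone wrong. The recruitment consequence depends on an antibody test being run, which the documents do not establish. Its size cannot be given. The study describes itself as hypothesis-generating and already narrows its population by BMI, language, autoimmune history and more, and no mechanism is offered by which hepatitis B antibody status would distort correlates of influenza response. Most of the 26 exclusions carry no stated reason, so the absence of one here is not itself a fault. The missing judgement clause applies equally to HIV and hepatitis C in the same item. The infection-screening purpose is an inference from that grouping. Known hepatitis B would probably come out in the medical history.

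All of that stands, and it limits the point. It does not remove it: a mandatory criterion, followed to the letter, excludes healthy vaccinated people, and the history and examination narrow the gap for current infection without closing it.

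Three stronger readings are tempting and are not supported:

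- *That the plan contradicts itself.* It does not; the three entries agree.
- *That vaccinated volunteers have been turned away, or infected ones enrolled.* The documents do not say which assay is used. The 24 subjects enrolled in year 1 do not reveal it either.
- *That the adjMFC slopes are biased or the study underpowered.* No route to bias is shown, and Table 2 is unaffected.

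**Conclusion.** The point holds as a defect in the eligibility text. Two statements are certain from the documents: the only named hepatitis B analyte is the surface antibody, and a positive result excludes without exception. Two consequences follow if the text is applied literally, given the premise that vaccination produces this antibody: healthy people vaccinated more than 14 days earlier are excluded, and current infection is not directly tested for.

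Whether the antibody is intended or is a naming slip cannot be settled from the documents. Severity is minor to moderate, with high confidence in the wording and low confidence in the practical size.

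**What to change.** Make the analyte in section 4.3 item 2, section 6.1 and Appendix A match the purpose of the criterion.

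- If the purpose is to exclude hepatitis B infection, name a surface antigen test in place of the antibody in all three places.
- If the antibody is intended, say so in section 4.3 and state how volunteers with vaccine-induced antibody are handled.

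The cost is a wording amendment in three places and possibly a change of assay on blood already drawn at screening. The sample size, Table 2 and the planned analyses stay as they are.
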